8.2 Statistical analysis of the secondary efficacy variables

The secondary efficacy variables will be analyzed for all subjects in the FAS.

All categorical variables (ie, ACR20/70 response and PASI75/90 response) will be analyzed for treatment effects using pairwise comparisons using the same logistic model as described in the secondary analysis of the primary variable ([Section 8.1.3](#)).

The responder rates for placebo, BKZ 16mg, BKZ 160mg w/ LD, BKZ 160mg, BKZ 320mg, and for each dose the odds ratios (differences to placebo), 95% CIs, and corresponding p-values from the logistic regression will be provided.

The categorical efficacy variables will be analyzed using observed cases as treated and imputed with NRI.

8.2.1 Derivation of Psoriasis Area and Severity Index (PASI), PASI75, PASI90, and PASI100

PASI will be assessed in all subjects with Baseline BSA affected by psoriasis $\geq 3\%$ determined by the method described in [Section 8.1.1.6](#) (ie, the BSA palm method).

The PASI is the most commonly used and validated assessment for grading the severity of psoriasis in clinical studies (Feldman, 2004). The PASI quantifies the severity and extent of the disease and weighs these with the percentage of BSA involvement.

Table 8–3: Body areas for calculation of percent BSA for PASI

Body area	Details of area	BSA	Degree of involvement of body area ^a
Head	Face, back of head	10%	0 to 6
Upper limbs	Left, right, upper lower, flexor surface, extensor surface	20%	0 to 6
Trunk	Front, back, groin	30%	0 to 6
Lower limbs	Left, right, upper lower, flexor surface, extensor surface, including buttocks	40%	0 to 6
Total		100%	

BSA=body surface area; PASI=Psoriasis Area and Severity Index

^a Where 0=none; 1=1% to <10% affected, 2=10% to <30% affected, 3=30% to <50% affected, 4=50% to <70% affected, 5=70% to <90% affected, 6=90% to 100% affected

The body is divided into 4 sections (head (h) (10% of a person's skin); arms (a) (20%); trunk (t) (30%); legs (l) (40%), [Table 8–3](#)). Each of these sections is scored by itself, and then the 4 scores are combined into the final PASI. For each section, the percent of area of skin affected (A), is estimated and then transformed into a grade from 0 to 6:

- 0% of involved area, grade: 0
- < 10% of involved area, grade: 1
- 10-29% of involved area, grade: 2
- 30-49% of involved area, grade: 3
- 50-69% of involved area, grade: 4
- 70-89% of involved area, grade: 5
- 90-100% of involved area, grade: 6

Within each body area, the severity is estimated by three clinical signs: redness (R), thickness (T), and scaliness (S) (each on a 5-point scale): 0=none, 1=slight, 2=moderate, 3=marked, and 4=very marked. The PASI is a measure of the average redness, thickness, and scaliness of the psoriatic skin lesions, multiplied by the involved psoriasis area score of the respective section, and weighted by the percentage person's skin for the respective section:

$$PASI = 0.1 * Ah * (Rh + Th + Sh) + 0.2 * Au * (Ru + Tu + Su) + 0.3 * At * (Rt + Tt + St) + 0.4 * Al * (Rl + Tl + Sl) \quad (11)$$

where

Rh, Ru, Rt, and Rl is the redness score of plaques on the head, upper limbs, trunk, and lower limbs;

Th, Tu, Tt, and Tl is the thickness score of plaques on the head, upper limbs, trunk, and lower limbs;

Sh, Su, St, and Sl is the scaliness score of plaques on the head, upper limbs, trunk, and lower limbs;

Ah, Au, At, and Al is the degree of involvement for the head, upper limbs, trunk, and lower limbs.

The PASI score ranges from 0 to 72 with a higher score indicating increased disease severity

In case up to 2 severity measurements are missing for a certain region, the average of the remaining will be utilized to substitute the missing(s). If the area of affected skin and/or all severity measurements for up to 2 body areas are missing, missing $(R+T+S) \times A$ for a body area will be substituted by the average of the available $(R+T+S) \times A$. Otherwise the PASI will be set to missing.

The PASI50, PASI75, PASI90, and PASI100 responses are based on at least 50%, 75%, 90%, and 100% improvement from Baseline in the PASI score.

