## 9.9 Psoriasis Area and Severity Index (PASI)

PASI will be assessed in all subjects with Baseline/Day 1 BSA affected by PSO  $\geq 3\%$  determined by the method described in Section 9.8 (ie, the BSA palm method).

The PASI is the most commonly used and validated assessment for grading the severity of psoriasis in clinical studies (Feldman, 2004). The PASI quantifies the severity and extent of the disease and weighs these with the percentage of BSA involvement.

The percent area of involvement (BSA%) is estimated across 4 body areas; head, upper limbs, trunk, and lower limbs and then transferred into a grade (Table 9-2).

The Investigator assesses the average redness, thickness, and scaliness of lesions in each body area (each on a 5-point scale); 0=none, 1=slight, 2=moderate, 3=marked, and 4=very marked.

The PASI score ranges from 0 to 72 with a higher score indicating increased disease severity.

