4.2 Handling of dropouts or missing data

4.2.1 Handling of missing data for efficacy analysis

The analysis for the binary primary, secondary, and other efficacy variables will use non-responder imputation (NRI) for handling missing data. In NRI, each subject with missing data or who has discontinued Double-Blind study treatment prior to Week 12 will be counted as a non-responder.

Sensitivity analysis will be performed for the secondary analysis of the primary variable (ACR50 response at Week 12) using MI assuming that missingness is missing at random (MAR). The MI method will be applied as follows:

1. Create a data set, sorted by treatment groups, of subjects with observed values and those needing estimation by multiple imputation. For the imputation step, missing values will be separated into non-monotone missing values (ie, intermittent missing values between completed assessments) and monotone missing values (ie, missing values after the patient dropped out). The procedure will sequentially estimate an imputation model for the ACR components at each post-Baseline visit where ACR components are collected, with geographic region, and prior TNF inhibitor exposure as covariates separated between the treatment groups.

- For the imputation of intermediate missing values, the missing ACR components in each data set will be filled in using the Markov-Chain Monte Carlo (MCMC) method with multiple chains and monotone imputing. A total number of imputations will be 100. The seed used for these imputations will be 2017.

Note: All other multiple imputation procedures described in this SAP will use this same seed as well.

Note: The imputation model based on the MCMC method will only allow continuous variables as predictors. Therefore, prior TNF inhibitor exposure and geographic region will be re-coded as indicator variables (with values of 0 or 1 for each level of the variable).

Note: To avoid that imputed values are outside of the pre-defined range of values for the ACR components (eg, HAQ-DI [0-3]) maximum and minimum values for imputed variable values are specified.

- If the intermediate missing data are imputed, the monotone missing data will be imputed for all patients with monotone regression including geographic region, and prior TNF inhibitor exposure as covariates. The dataset is the output dataset of the partial imputation. Since this dataset already has 100 imputed values at each visit, only one imputation will be performed.

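### SAP 8.2.1 applies its missing-severity rule without regard to recorded area, so a clear body area with blank severity can give a wrong or missing PASI

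*SAP*

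**What the plan says.** SAP 8.2.1 builds the PASI from four body areas. Each contributes a weight (0.1 head, 0.2 upper limbs, 0.3 trunk, 0.4 lower limbs) times an area grade A from 0 to 6 times the sum of redness, thickness and scaliness, R+T+S. A clear area has its own valid grade: "0% of involved area, grade: 0". Each sign is graded "0=none, 1=slight, 2=moderate, 3=marked, and 4=very marked".

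The section then gives three missing-data steps:

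- If one or two of the three signs are blank within an area, they take the average of the signs present.
- "If the area of affected skin and/or all severity measurements for up to 2 body areas are missing", the product "for a body area will be substituted by the average of the available" products.
- "Otherwise the PASI will be set to missing".

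SAP 8.2 analyses PASI75 and PASI90 with non-responder imputation (NRI), which SAP 4.2.1 defines: "In NRI, each subject with missing data or who has discontinued Double-Blind study treatment prior to Week 12 will be counted as a non-responder".

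Neither document makes an exception for an area with recorded grade 0, and neither says how severity is to be recorded there.

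**The concern.** The product A x (R+T+S) is fixed at 0 once A = 0, so blank severity fields leave nothing unknown. The rule does not look at A when severity is blank: its and/or wording makes three blank signs a sufficient trigger. A known zero is then replaced by a positive number whenever the other available areas are not all clear, or the whole score is discarded.

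Zero-area regions should not be rare. PASI is scored from 3% of body surface upwards, about three palms, so some areas may be clear even at Baseline, and more would be expected after effective treatment. The signs describe lesions, so a site facing a clear area might enter 0 or might enter nothing.

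PASI75 and PASI90 at Week 12 are secondary efficacy variables. PASI90 also enters the composite with ACR50 and the Week 48 comparison in SAP 8.3 that is meant to gauge bias from possible unblinding. At 40 subjects per arm at most in the psoriasis subgroup, one misclassified subject moves an arm's rate by at least 1/40 = 2.5 percentage points.

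**Working it through.** **Inputs.** Weights, grades and equation (11) are from SAP 8.2.1: PASI = sum over areas of w x A x (R+T+S). The patient patterns below are illustrative; the documents give none.

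**1. The plan's own figure.** Maximum = (0.1+0.2+0.3+0.4) x 6 x (4+4+4) = 72; minimum = 0. The stated range of 0 to 72 reproduces.

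**2. Two clear areas, severity blank.** Head and trunk A = 0 with R, T, S blank; upper and lower limbs A = 2, R+T+S = 6.

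- Limb products: 2 x 6 = 12 each.
- Determinate score: 0.2 x 12 + 0.4 x 12 = 7.2.
- Literal rule: the mean of the available products is 12, so 12 x (0.1+0.2+0.3+0.4) = 12.0.
- Ratio: 12.0/7.2 = 1.67, an inflation of 67%.

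**3. If that visit is Baseline.** The same subject at Week 12 has only the lower limbs left, A = 1 and R+T+S = 2, so PASI = 0.4 x 2 = 0.8. True improvement is 1 - 0.8/7.2 = 88.9%: PASI75 yes, PASI90 no.

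- Week 12 clear areas entered as 0: 1 - 0.8/12.0 = 93.3%, so a false PASI90 response.
- Week 12 clear areas left blank: three areas count as missing, the PASI is missing and NRI scores a failure, so the PASI75 response is lost.

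One subject can therefore be misclassified in either direction.

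**4. If blanks occur only at Week 12.** Assume a complete Baseline: head and upper limbs A = 2 and sum 6, trunk A = 3 and sum 6, lower limbs A = 3 and sum 7. Then PASI = 0.1 x 12 + 0.2 x 12 + 0.3 x 18 + 0.4 x 21 = 17.4.

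| Week 12 areas with A = 0 and blank severity | Literal rule | With A = 0 giving 0 |
|---|---|---|
| Lower limbs (other products: head 2, upper limbs 1, trunk 3) | 1.3 + 0.4 x 2 = 2.1; 87.9% | 0.2+0.2+0.9 = 1.3; 92.5% |
| Trunk and lower limbs (head 4, upper limbs 5) | 1.4 + 0.7 x 4.5 = 4.55; 73.9% | 0.4+1.0 = 1.4; 92.0% |
| All but head (head 3) | missing, non-responder | 0.3; 98.3% |
| All four | missing, non-responder | 0; 100% |

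The first row loses PASI90; the second loses PASI75 and PASI90; the third loses both by missingness; the fourth also loses PASI100.

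**5. When the rule does no harm.** If the clear areas are scored R = T = S = 0, the literal rule gives 0.3 (98.3%) and 0 (100%) for the last two rows, the same as the corrected rule. If only one or two signs are blank in a clear area, the within-area average is multiplied by A = 0 and the product is still 0. Harm needs all three signs blank in an area with A = 0.

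**The case against.** The best defence is that the situation should not arise. Protocol 9.9 reads "The Investigator assesses the average redness, thickness, and scaliness of lesions in each body area (each on a 5-point scale", and both documents supply a grade for none. A clear area therefore has a proper entry of 0, equation (11) gives 0, and no missing-data rule is reached. The SAP also defines PASI100, so its authors expected a fully clear subject to have a score. This stands as evidence about likely practice. It does not tell a programmer what to do with a blank, and the same SAP recognises elsewhere that a blank can mean unaffected: under 8.3.6 an empty dactylitis page at Baseline is read as no digits involved.

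Second, what the rule replaces is a missing product, and a product with A = 0 can be regarded as known. That reading is possible, but the trigger names missing severity as enough. Two competent programmers could reach opposite responder status.

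Third, PASI does not enter the primary ACR50 analysis, and SAP 3.10 removes fixed-sequence testing from the secondary variables. This limits the importance but does not make the rule right.

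A reader might go further and infer that subjects clear on three or four areas are in fact being scored as failures, or that the rule shrinks the treatment effect because clear skin is concentrated in the active arms. The documents support neither. The first needs blank entries that no section describes. The second overlooks Baseline, where filling enlarges the denominator and inflates improvement.

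**Conclusion.** Wrong as written, low impact. SAP 8.2.1 states a rule that, taken literally, gives a wrong value for a determinate score (12.0 instead of 7.2 in the example) or discards a score of 0.3 or 0 and counts the subject as a non-responder. This rests on one assumption that the documents do not settle: that redness, thickness and scaliness are all left blank in some areas with grade 0. The scoring instructions suggest zeros, in which case there is no effect. The PASI page of the CRF is not shown, no rate of blank entries can be derived, and so the number of subjects affected cannot be estimated. The direction of any net bias is also not established, because blanks at Baseline favour response and blanks at Week 12 work against it.

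**What to change.** Insert in SAP 8.2.1, before the missing-data steps: if A = 0 for a body area, then (R+T+S) x A = 0 for that area regardless of the severity entries, at Baseline and at all post-Baseline visits; the substitution steps apply only to areas where A > 0 or A is missing.

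Confirm how the CRF records severity when the area is 0, and count the area-visits with A = 0 and all three signs blank, by arm, at Baseline and Week 12. If there are none, no result changes.

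The cost is one sentence and a rerun of the PASI derivation. It is not quite free. SAP 4.3.1 has the Week 12 interim cover the secondary efficacy analyses with treatment codes released to sponsor personnel, and 4.3.1.1 describes that interim as done. The amendment should therefore be recorded as a derivation change made after the Week 12 interim analysis, alongside the changes already listed in 4.3.1.1 and 4.3.2.1, with any subject whose PASI response changes identified.

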8.3 Analysis of other efficacy variables

All other efficacy variables will be analyzed for all subjects in the FAS, DBRS, ESS, cDBRS, cESS, and DBS.

All binary variables will be summarized using frequency tables by each visit. All continuous variables will be summarized using descriptive statistics by each visit.

The Hospital Anxiety and Depression Scale (HADS) will be analyzed separately for HADS-A and HADS-D. The summary statistics for HADS-A and HADS-D will be presented in two different tables.

Subgroup of subjects will be used for the analyses of mNAPSI, MASES, and LDI. The MASES will be analyzed for subjects with enthesitis at Baseline ($MASES > 0$). The LDI will be summarized for subjects with dactylitis at Baseline ($LDI > 0$) and the mNAPSI will be analyzed on a subgroup of subjects with nail disease at Baseline ($mNAPSI > 0$).

CDF plots of PSAID-9 change from Baseline to Week 12 and from Week 12 to Week 48 by treatment group will be presented as well as a frequency table with number of subjects with $PSAID-9 \leq 3$.

Times series plots will be provided for the response rate for the primary and secondary efficacy variables. The plots will show the weekly response rate over the first 12 weeks.

Time to onset of ACR20/50 response will be estimated and presented using the Kaplan-Meier product-limit method for each treatment. Time to a given response will be defined as the length in weeks from Baseline until the first date when the response is achieved. Following derivation will be used: Days from Baseline until the first date divided by 7. There will be no rounding for the Kaplan Meier estimates. Subjects who discontinue study prior to achieving a response will be censored at the date of study discontinuation. Subjects who reach the Week 12 visit without achieving a response will be censored at the date of the Week 12 visit. Missing response data will be imputed with NRI.

The median time to response including the two-sided 95% CI will be calculated for each treatment. Between groups differences (each bimekizumab dose versus placebo) will be analyzed using a log-rank test stratified by geographic region and prior TNF inhibitor exposure. Missing response data will be imputed with NRI.

Summary tables will be presented for the time to onset of ACR20 response and ACR50 response including following information: number of subjects achieving ACR20/ACR50 response, number of subjects censored, descriptive statistics (minimum, 25th percentile, median, 75th percentile, maximum) for the Kaplan-Meier estimates including the p-value (difference to placebo). Additional Kaplan-Meier Plots will be provided.

All other efficacy variables will be analyzed using observed cases as treated and imputed with NRI for binary variables and multiple imputation for categorical/continuous variables.

Subjects in the ESS who discontinue with bimekizumab treatment during the Dose-Blind Period will be treated as missing and categorical/continuous variables will be imputed.

In order to assess the potential bias of the potentially unblinded subjects based on data, the results of the final analysis will be utilized. Results of the ACR50 and PASI90 response of the rerandomized 320mg and 160mg treatment group at Week 48 will be compared to the potentially unblinded, randomized 320mg and 160mg treatment groups. If the percentage of ACR50 and PASI90 responders is comparable as assessed by overlapping 95% confidence intervals, the potential bias is estimated to be at minimum.

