### 15.3.2.2 Analysis of the other efficacy variables

All other efficacy variables in the Double-Blind Period will be analyzed for all subjects in the FAS. For the Dose-Blind period, other efficacy variables will be analyzed for all subjects in the DBRS and ESS.

All categorical variables will be summarized using frequency tables by each visit.

All continuous variables will be summarized using descriptive statistics by each visit.

Time to onset of ACR20/50 response will be estimated and presented using the Kaplan-Meier product-limit method for each treatment. Time to a given response will be defined as the length in days from Baseline until the first date when the response is achieved. Subjects who discontinue study treatment prior to achieving a response will be censored at the date of study treatment discontinuation. Subjects who reach the Week 12 visit without achieving a response will be censored at the date of the Week 12 visit.

The median time to response including the two-sided 95% confidence interval (CI) will be calculated for each treatment. Between group differences (each bimekizumab dose versus placebo) will be analyzed with the log-rank statistic.

All other efficacy variables will be analyzed using observed cases as treated and imputed with NRI for binary variables and multiple imputation for categorical/continuous variables (see Section 15.7).

Subjects in the ESS who discontinue with bimekizumab treatment during the Dose-Blind Period will be treated as missing and categorical/continuous variables will be imputed.

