3.10 Changes to protocol-defined analyses

The PK variables total body clearance (CL/F) and volume of distribution (V/F) will be analyzed separately. CL/F and V/F variables were removed from the PK variable list.

Following two subgroup analyses were added: time since first diagnosis of PsA and body weight.

Instead of stopping the pairwise testing of each bimekizumab dose versus placebo once it failed to reach significance at a significance level of $\alpha=0.05$, the pairwise testing will continue and further pairwise comparisons are seen as non-significant.

No fixed sequence testing will be used for the secondary efficacy variables.

The other efficacy variable modified MDA was added to the analysis. The definition for the modified MDS is available in [Section 8.3.1](#).

Time to a given response is defined as the length in weeks from Baseline until the first date when the response is achieved. In the definition the length was changed from days to weeks due to easier interpretation.

Two addition analyses were added in the section analysis of other efficacy variables. A frequencies table counting the number of subjects with $\text{PSAID-9} \leq 3$ as well as cumulative distribution function (CDF) plots of PSAID-9 change from Baseline to Week 12 and Week 12 to Week 48 by treatment group.

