8.1.2 Primary analysis of the primary efficacy variable

The primary efficacy variable (ACR50 at Week 12) will be analyzed for all subjects in the FAS.

The dose-response relationship between treatment and ACR50 response will be assessed with an ordered categorical analysis using a nonparametric correlation statistic of Mantel and Haenszel

(Mantel and Haenszel, 1959) and modified ridit scores (Bross, 1958) with the corresponding p-value.

The analysis will include geographic region and prior TNF inhibitor exposure as stratification factors. Prior TNF inhibitor exposure will be used as a stratification factor as it may have an impact on efficacy. The use of geographic region as a stratification factor is intended to combine study centers in similar geographic regions. The geographic regions are defined in [Section 3.8](#). The correlation between dose and ACR50 response will be evaluated at a two-sided significance level of $\alpha=0.05$. This evaluation of dose-response will constitute the primary efficacy analysis.

Bimekizumab 160mg with loading dose will be excluded from the dose-response analysis. A table will present the responder rates for placebo, BKZ 16mg, BKZ 160mg, BKZ 320mg, and the correlation statistic of Mantel and Haenszel (ridit score) with the corresponding p-value.

NRI will be used to account for missing data in the primary analysis. That is, subjects with a missing ACR score at Week 12 or who discontinued study treatment prior to the Week 12 visit will be considered non-responders for the primary analysis.

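### SAP 8.3 moves the censoring point for time to ACR20/50 response from treatment discontinuation to study discontinuation without listing the change, and does not settle whether off-drug responses count as events

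*SAP*

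**What the plan says.** Time to ACR20/50 response is an 'other' efficacy variable. It is estimated by Kaplan-Meier, and each dose is compared with placebo by a log-rank test, stratified in the SAP.

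- **Protocol 15.3.2.2:** "Subjects who discontinue study treatment prior to achieving a response will be censored at the date of study treatment discontinuation".
- **SAP 8.3:** "Subjects who discontinue study prior to achieving a response will be censored at the date of study discontinuation". For those who get to the end of the period: "Subjects who reach the Week 12 visit without achieving a response will be censored at the date of the Week 12 visit". For gaps in the data: "Missing response data will be imputed with NRI". This last sentence is given for the Kaplan-Meier estimates and again for the log-rank test.
- **SAP 4.2.1, scope of NRI:** "The analysis for the binary primary, secondary, and other efficacy variables will use non-responder imputation (NRI) for handling missing data". Definition: "each subject with missing data or who has discontinued Double-Blind study treatment prior to Week 12 will be counted as a non-responder".
- **SAP 8.1.2, primary analysis:** "subjects with a missing ACR score at Week 12 or who discontinued study treatment prior to the Week 12 visit will be considered non-responders".
- **SAP 3.10, the only change from the protocol listed for this variable:** "In the definition the length was changed from days to weeks due to easier interpretation".

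SAP 4.3.1.1 lists differences between the Week 12 interim and the current plan. It mentions the CRP and hs-CRP baseline definition changed by Amendment 4, but not censoring. SAP 4.3.1 includes time to ACR20 and ACR50 response in that interim.

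**The concern.** In many trials, stopping drug and leaving the study fall on nearly the same day, and the two censoring rules would give nearly the same answer. Here they need not. Protocol 6.3 asks subjects taken off treatment before Week 12 under criteria 4 to 10 to come back for the Week 12 assessments, and SAP 3.5 keeps those data as Week 12 data. Such a subject is off drug, still in the study and, under SAP 8.3, still in the risk set.

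The SAP does not say what happens if that subject meets ACR50 at Week 12. The censoring sentence lets the response stand as an event for the randomized arm. NRI as defined in 4.2.1 makes the subject a non-responder. The two readings give different Kaplan-Meier curves and log-rank tests from the same data, so the choice would fall to whoever programs the analysis. SAP 8.1.5 places all-available Week 12 data, off-drug assessments included, in a sensitivity analysis and warns that placebo subjects on another active medication may confound it. Section 8.3 could bring the same data into the main curve with no such label.

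A second inconsistency lies in the same paragraph. Subjects who leave the study are censored when they leave, yet missing response is said to be imputed as non-response. These are two different treatments of the same people.

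**Working it through.** The plan gives no figure to reproduce for this variable. The check is a comparison of the rules, followed by an illustration.

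**Rules side by side, for a subject who stops drug without a response and returns at Week 12 as a responder**

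| Rule | Outcome |
|---|---|
| Protocol 15.3.2.2 | Censored on the day treatment stops |
| SAP 8.3, observed response is not missing | Event at Week 12 |
| SAP 8.3 with NRI as defined in 4.2.1 | Non-responder, censored at Week 12 |
| Primary analysis, SAP 8.1.2 | Non-responder |

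**Illustration.** The 40 subjects per arm come from protocol 5.1.8. Everything else is assumed: 22 on-drug ACR50 responders, first seen at Week 4 (6), Week 8 (8) and Week 12 (8); *m* subjects who stop drug between Weeks 4 and 8 without a response and return at Week 12; *r* of them respond off drug. The NRI rate is 22/40 = 55.0%.

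- Protocol rule: 1 − (34/40) × (1 − 8/(34 − m)) × (1 − 8/(26 − m)). For m = 4: 1 − 0.85 × (22/30) × (14/22) = 60.3%.
- SAP rule, off-drug responses counted: nobody is censored before Week 12, so the estimate is (22 + r)/40. For r = 4: 26/40 = 65.0%.
- SAP rule with NRI: 22/40 = 55.0% for every m.

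| m | Protocol rule | SAP, all m respond and count | SAP with NRI |
|---|---|---|---|
| 1 | 56.2% | 57.5% | 55.0% |
| 2 | 57.5% | 60.0% | 55.0% |
| 4 | 60.3% | 65.0% | 55.0% |

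Each off-drug response that counts adds 1/40 = 2.5 points. The direction against the protocol rule is not fixed. With m = 4, counting gives 60.0% for r = 2 (below 60.3%) and 62.5% for r = 3 (above it). The same step applies to placebo: an arm with 3 on-treatment responders (3/40 = 7.5%) moves to 10.0% with one off-drug responder and 12.5% with two. The log-rank test was not recomputed; it changes because both the events and the risk sets change.

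**Study dropouts.** Take 40 subjects, 3 events before Week 4, 4 subjects who leave the study at Week 4 without a response, and 14 events among the remaining 33. With censoring at departure, the estimate is 1 − (37/40) × (19/33) = 46.7%. Carried as non-responders to Week 12, it is 17/40 = 42.5%, which is 4.2 points lower. These four also stop treatment when they leave, so the protocol's rule gives 46.7% as well.

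**The case against.** The strongest reply is that the SAP already does the sensible thing. Section 8.3 invokes NRI for both the curves and the test, ACR response is binary, and 4.2.1 applies NRI to other efficacy variables and to anyone who stopped double-blind treatment. On that reading, off-drug responses never count, and in the first illustration the SAP rule equals the NRI rate while the protocol rule exceeds it. This stands as a possible reading. A reader might infer that off-drug responses will certainly be counted as events; the documents do not support that. They do not exclude it either: 8.3 applies NRI to missing responses, an observed one is not missing, and 4.2.1 is written for binary variables rather than a time to event.

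Other parts of the reply also stand:

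- The gain from censoring dropouts (46.7% against 42.5%) comes equally from the protocol's rule. It is not an effect of the SAP change.
- A reader might infer that the change is what stops the curves being read with the primary result. It is not. A subject who responds at Week 4 and stops drug at Week 5 is an event under both censoring rules and a non-responder in the primary analysis.
- Counting data after treatment stops is a legitimate question, and SAP 8.1.5 asks it as a sensitivity analysis.
- The change is not concealed. The Amendment 4 log shows the word for treatment struck out in both places, so it was deliberate. A reader might infer from its date, after an interim at which most sponsor staff received treatment codes, that results prompted it. The documents show the order of events, not a reason of that kind.

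**Conclusion.** The conflict between protocol 15.3.2.2 and SAP 8.3 is real, and SAP 3.10 and 4.3.1.1 omit it. SAP 8.3 leaves open whether off-drug responses are events, and it prescribes both early censoring and non-response for study dropouts. On the assumptions shown, with 1 to 4 of 40 subjects stopping drug and all of them responding later, the two readings of the SAP differ by 2.5 to 10.0 points at Week 12 (57.5% to 65.0% against 55.0%).

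The real size cannot be stated. The documents give no rate of treatment discontinuation and no rate of off-drug response, and the return request covers only criteria 4 to 10, one of which (9) also requires withdrawal from the study. Reach is limited: the variable lies outside the fixed testing sequence, and the primary ACR50 result and its Type I error control do not change.

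**What to change.** In SAP 8.3, count as events only responses observed before study treatment discontinuation. Carry subjects who stop treatment or leave the study without a response as non-responders, censored at the planned Week 12 day. This gives one rule, consistent with NRI in 4.2.1, and settles both inconsistencies. It does not restore the protocol's rule, which censors on the day treatment stops, so list it in 3.10 as a change from the protocol. In 4.3.1.1, note any difference from the rule used at the Week 12 interim. If an analysis that counts off-drug responses is wanted, label it a sensitivity analysis.

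The cost is SAP wording and one derivation. Kaplan-Meier response estimates may be slightly lower and median times slightly longer.
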